3. Male subjects who are sexually active with female partners of childbearing potential must agree to use a condom with spermicide and to use (or have their partner use) 1 other approved method of highly effective contraception from the initiation of the study and until at least 90 days after the last dose of investigational product as listed in Inclusion Criterion #2.
 4. Male patients must refrain from sperm donation from the initiation of the study and until at least 90 days after the last dose of investigational product.
 5. Must provide written informed consent and agree to comply with the study protocol.

Key Exclusion Criteria:

1. Any history or presence in the last 30 days, before rolling over to this study, of other concomitant liver diseases, including any of the following:
 - Hepatitis C virus (HCV) infection with positive RNA
 - Active hepatitis B virus (HBV) infection; however, subjects who have seroconverted (hepatitis B surface antigen negative [sAg-], hepatitis B surface antibody positive [sAB+]; hepatitis B e-antigen negative [eAg-], hepatitis B e-antibody positive [eAb+]; HBV DNA negative) may be included in this study after consultation with the Medical Monitor and Sponsor Medical Monitor
 - Subjects should be excluded if positive HBV DNA or HCV RNA
 - Primary sclerosing cholangitis
 - Alcoholic liver disease
 - Definite autoimmune liver disease or PBC-autoimmune hepatitis (AIH) overlap
 - Metabolic dysfunction-associated steatohepatitis (MASH)
 - Gilbert's Syndrome (due to interpretability of bilirubin levels)
 - Rare liver conditions such as Wilson's disease, hemochromatosis, alpha-one anti-trypsin deficiency, or other conditions identified by the Principal Investigator
2. Clinical complications of PBC including:
 - Prior liver transplantation
3. Any history or presence in the last 30 days, before rolling over to this study, of any one of the following decompensating events:
 - Child-Pugh (CP) Score ≥ 7

- Clinical evidence of decompensated liver disease or evidence of portal hypertension, including but not limited to:
 - Varices (including a history of esophageal varix ligation or asymptomatic esophageal varices by endoscopy)
 - Ascites/hepatic hydrothorax
 - Spontaneous bacterial peritonitis
 - Hepatic encephalopathy
 - Jaundice (with total bilirubin >3 mg/dL [$>51.3 \mu\text{mol/L}$])
 - Biochemical evidence of hepatic impairment, decompensation, or injury including at least one of the following:
 - Total bilirubin >ULN

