- Unscheduled visits as needed in the event of signs or symptoms of potential hepatic and/or muscular injury or decompensation or if laboratory alerts have been triggered

It is important that the laboratory assessments be completed as required and that the central laboratory be used for assessments whenever possible. In the event that a subject cannot return to the clinic for a scheduled or unscheduled visit, or there is an event that triggers a need for an immediate assessment, the use of a local lab is permissible at the discretion of the Investigator. In these cases, the Investigator will obtain the laboratory results and the laboratory normal ranges.

The process for assessing criteria is presented in Figure 2, and the specific threshold(s) for each laboratory analyte to trigger investigational product interruption are summarized in Table 5.

Figure 2: Management Algorithm for Potential Hepatic and/or Muscular Injury

CK=creatine kinase; INR=international normalized ratio; IP=Investigational Product; PK=pharmacokinetic

Notes: Laboratory assessments include: ALT, ALP, AST, GGT, direct and total bilirubin, INR, and CK.

PK sampling should be conducted within 7 days of IP interruption; close monitoring including physical exams and repeat biochemistry labs should occur as often as deemed appropriate by the Investigator (Table 4).

Table 4: Laboratory Criteria for Monitoring of Potential Hepatic and Muscular Injury for Interruption^a of Investigational Product

Baseline ^b	Treatment Emergent	Liver Signs and Symptoms ^c
Any value	Any hepatic enzyme elevation (TB, ALP, AST, ALT, GGT)	Yes
ALT or AST Normal	ALT or AST ≥ 3 x ULN and TB ≥ 2 x BL	Yes or No
	ALT or AST ≥ 3 x ULN and INR >1.5	Yes or No
	ALT or AST ≥ 5 x ULN and Any TB	Yes or No
ALT or AST Elevated	ALT or AST ≥ 2 x BL and TB ≥ 2 x BL	Yes or No
	ALT or AST ≥ 2 x BL and INR >1.5	Yes or No
	ALT or AST ≥ 3 x BL (or ≥ 300 U/L, whichever occurs first) and Any TB	Yes or No
TB \leq ULN	TB ≥ 2 x BL and $>$ ULN	Yes or No
TB $>$ ULN	TB ≥ 1.5 x BL or ≥ 3.0 mg/dL, whichever occurs first	Yes or No
ALP \leq ULN	ALP ≥ 2 x BL and $>$ ULN	Yes or No
ALP $>$ ULN	ALP ≥ 2 x BL or ≥ 1000 U/L, whichever occurs first	Yes or No
CK	≥ 5 x ULN or ≥ 3 x ULN with symptoms of rhabdomyolysis ^{d,e}	N/A

BL=baseline; CK=creatinine kinase; DILI=drug-induced liver injury; INR=international normalized ratio; IP=investigational product; N/A=not applicable; TB=total bilirubin

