^a Interrupt study drug; Initiate workup of competing etiologies and close monitoring (repeat labs and exam 2-3 times per week), including repeat labs initially.

- Study drug can be restarted after a minimum of 30 days if another etiology is identified, liver enzymes return to baseline, lab abnormalities are determined not to be due to DILI, no symptoms, and approved by the Medical Monitor and Investigator.
- If study drug is restarted after 30 days, repeat labs in 2-5 days for ALT, AST, and TB or 7-10 days for ALP as indicated and continue close monitoring.

^b New baseline values for DILI monitoring for ALT, AST, ALP, TB should be determined based upon average of Month 3 and Month 6 values if average is $>50\%$ decrease from original baseline. Adapted from [Palmer 2020](#).

^c Liver signs and symptoms to include: new onset severe fatigue or significant worsening of baseline fatigue; new onset severe pruritus or significant worsening on baseline pruritus; nausea, vomiting, right upper quadrant pain; fever, rash, or $>5\%$ eosinophilia; new onset of hepatic decompensation (e.g., ascites, variceal bleeding, hepatic encephalopathy).

^d Symptoms of rhabdomyolysis may include muscle swelling; weak, tender or sore muscles; dark urine; fever; tachycardia; nausea and vomiting; confusion; dehydration; or abdominal pain.

^e If IP interrupted due to CK trigger, closely monitor CK and creatinine/renal function in addition to liver biochemistries every 2 weeks until values return to baseline levels; same criteria apply to considering re-initiation of IP. CK levels should be assessed in patients reporting symptoms of rhabdomyolysis, and investigational product should be discontinued if markedly elevated CK levels (≥ 5 x ULN) occur or myopathy is diagnosed.

It should be noted that it is difficult to recognize every potential marker of hepatic deterioration or muscular injury. There is no substitute for good medical judgment. Investigators will be reminded to be cautious and mindful in their evaluation of subjects' symptoms, signs, and laboratory results. However, for example, a single abnormal laboratory analyte result may be artifactual; accordingly, Investigators will be allowed to implement an alternate follow-up procedure if considered appropriate based on their medical judgement but only after documented agreement with the Sponsor's Medical Monitor.

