8.3. Subject Exclusion Criteria

1. Any history or presence in the last 30 days, before rolling over to this study, of other concomitant liver diseases, including any of the following:
 - Hepatitis C virus (HCV) infection with positive RNA
 - Active hepatitis B virus (HBV) infection; however, subjects who have seroconverted (hepatitis B surface antigen negative [sAg-], hepatitis B surface antibody positive [sAB+]; hepatitis B e-antigen negative [eAg-], hepatitis B e-antibody positive [eAb+]; HBV DNA negative) may be included in this study after consultation with the Medical Monitor and Sponsor Medical Monitor
 - Subjects should be excluded if positive HBV DNA or HCV RNA
 - PSC
 - Alcoholic liver disease
 - Definite autoimmune liver disease or PBC-AIH overlap
 - MASH
 - Gilbert's Syndrome (due to interpretability of bilirubin levels)
 - Rare liver conditions such as Wilson's disease, hemochromatosis, alpha-one anti-trypsin deficiency, or other conditions identified by the Principal Investigator
2. Clinical complications of PBC including:
 - Prior liver transplantation
3. Any history or presence in the last 30 days, before rolling over to this study, of any one of the following decompensating events:
 - CP Score ≥ 7
 - Clinical evidence of decompensated liver disease or evidence of portal hypertension, including but not limited to:
 - Varices (including a history of esophageal varix ligation or asymptomatic esophageal varices by endoscopy)
 - Ascites/hepatic hydrothorax
 - Spontaneous bacterial peritonitis
 - Hepatic encephalopathy
 - Jaundice (with total bilirubin >3 mg/dL [>51.3 $\mu\text{mol/L}$])
 - Biochemical evidence of hepatic impairment, decompensation, or injury including at least one of the following:
 - Total bilirubin $>\text{ULN}$

- INR >1.7
 - Albumin <3.5 g/dL
 - MELD >12
 - ALT >5x ULN
 - Known or suspected HCC
 - Prior trans-jugular intrahepatic portosystemic or peritoneovenous shunt procedure
 - Hepatorenal syndrome (type I or II) or serum creatinine >1.5 mg/dL (135 µmol/L) or estimated glomerular filtration rate (eGFR) <60 mL/min from the last lab assessment/visit in parent study, before transitioning to Study 977-311
 - Portopulmonary hypertension
 - Hepatopulmonary syndrome
4. Medical conditions that may cause non-hepatic increases in ALP (e.g., Paget's disease) or that may diminish life expectancy to <2 years, including known cancers (except carcinomas in situ or other stable, relatively benign conditions)

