18. Treatment with the following medications 30 days before Day 1 of Study 977-311, or plans to use these medications during the study: azathioprine, colchicine, cyclosporine, methotrexate, mycophenolate mofetil, pentoxifylline, rifampicin, statins, budesonide and other systemic corticosteroids (short-term use up to 2 weeks is permitted), monoamine oxidase inhibitors (MAOIs), and potentially hepatotoxic drugs (including α -methyl-dopa, sodium valproic acid, isoniazid, and nitrofurantoin)
19. Treatment with the following medications within 12 months before Day 1 of Study 977-311, or plans to use these medications during the study: antibodies or immunotherapy directed against interleukins or other cytokines or chemokines
20. Participation in a study of another investigational medicine or device within 30 days before Day 1 of Study 977-311 (except for Study 747-213, Study 747-214, or other eligible Sponsor study)
21. History of or ongoing alcohol or drug abuse within 1 year before Day 1 of Study 977-311. Subjects with moderate alcohol use within 3 months prior to the last visit in parent study, before transitioning to Study 977-311, will be excluded from this study. Moderate alcohol consumption is defined as 1 standard drink per day for women and 2 drinks per day for men; whereby 1 standard drink is equivalent to: 12 oz beer (5% alcohol), 5 ounces of wine (12% alcohol), or 1.5 ounces of 80 proof (40% alcohol)
22. History of noncompliance with medical regimens, or is considered by the Principal Investigator not able to meet the requirements as specified in the protocol from Day 1 throughout the duration of the study
23. Blood or plasma donation within 30 days before Day 1
24. Mental illness or other condition which may impair decision making, such that the validity of informed consent or ability to be compliant with the study is uncertain
25. A CK value on Day 1 of Study 977-311 $\geq 5 \times$ ULN or any abnormal laboratory value that is considered CS in the opinion of the Principal Investigator and Sponsor at the last visit in parent study, before transitioning to Study 977-311
26. Known or suspected nephrotic syndrome in the last 30 days, before rolling over to this study, based on the following diagnostic criteria (both Type 1 and Type 2):
 - Proteinuria, spot urine protein: albumin/creatinine ratio (ACR) of >300 mg/mmol (subjects with normal renal function and ACR values analyzed to be below the lower limits of detection are permitted)

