10.3. Clinical Laboratory Evaluations

Laboratory parameters will be summarized in both conventional and standard international system of units using descriptive statistics at Baseline and at each on-study evaluation. Baseline is defined as the mean of all available evaluations prior to the first administration of investigational product.

The normal ranges of the selected lab parameters are defined below. The abnormal indicators of the selected lab parameters will be derived based on these normal ranges (inclusively):

- ALP 44-122 U/L
- ALT 0-45 U/L
- AST 0-45 IU/L
- GGT 0-65 IU/L (male) 0-60 IU/L (female)
- Total Bilirubin 1.71-12.3 umol/L
- Direct Bilirubin 0-0.4 mg/dL
- Cholesterol 0-169 mg/dL (age ≤19), 0-199 mg/dL (age >19)
- LDL 0-109 mg/dL (age ≤19), 0-99 mg/dL (age >19)
- HDL >39 mg/dL
- Creatinine 0.57-1.27 mg/dL
- Creatine 0.0-0.7 mg/dL (male) 0.1-1.0 mg/dL (female)
- CK 41-439 U/L (male, age 18-50 years old), 41-331 U/L (male, age 51-80 years old),

32-182 (female, age 18-80 years old)

For the other lab parameters, the normal ranges and abnormal indicators are based on the values in the data from the central or local labs.

In addition, shift tables (i.e., low-normal-high at Baseline versus low-normal-high at post-Baseline visit in a 3-by-3 contingency table) from Baseline to worst value, last value, and at each scheduled post Baseline visit will be provided for hematology and serum chemistry to assess changes in laboratory values from Baseline to each on-study evaluation from the central or local labs. The subjects meeting Hy's law criteria (defined as AST or ALT ≥ 3 xULN together with total bilirubin ≥ 2 xULN at any timepoint) will be summarized by visit.

Urine chemistry and urinalysis results will not be summarized but will be provided in a data listing.

All clinical laboratory data (including central and local) will be presented in by-subject data listings.

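### The SAP's Hy's law count takes no account of baseline enzymes, so a subject who enters with ALT or AST at 3x ULN or more can be tabulated as a case on a bilirubin rise alone

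*SAP*

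**What the plan says.** **The count.** The SAP 10.3 sentence opening "The subjects meeting Hy's law criteria (defined as AST or ALT" requires at least 3x ULN for one enzyme with total bilirubin of at least 2x ULN, and closes with "at any timepoint) will be summarized by visit". It has no condition on baseline or on change from baseline. The same section fixes the ULN at 45 for ALT and for AST, and gives "Total Bilirubin 1.71-12.3 umol/L".

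**Entry.** Exclusion 3 (Protocol 8.3 and synopsis) has a laboratory list headed "Biochemical evidence of hepatic impairment, decompensation, or injury including at least one of the following". It names "Total bilirubin >ULN", INR, albumin, MELD, and ALT above 5x ULN. AST is not on it. Exclusion 25 adds a judgement-based screen for "any abnormal laboratory value that is considered CS in the opinion of the Principal Investigator and Sponsor". Under Protocol 9.7.2.2, out-of-range Day 1 results are settled case by case before dosing.

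**Monitoring.** Protocol Table 4 (Section 7.4.2), which governs interruption of study drug, does use baseline. Normal baseline enzymes are judged by multiples of ULN. In the rows labelled "ALT or AST Elevated" the combined criterion is an enzyme of at least 2x baseline with bilirubin of at least 2x baseline. Footnote b begins "New baseline values for DILI monitoring for ALT, AST, ALP, TB should be determined" and resets the baseline to the Month 3 and Month 6 average when that average has fallen by more than half. A separate row, for baseline bilirubin at or below ULN, is met by bilirubin at least 2x baseline and above ULN, whatever the enzymes do.

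**The concern.** A Hy's law table is read as a count of subjects in whom enzymes and bilirubin rose together on treatment. Here the enzyme half can already be present at entry. In such a subject a later bilirubin rise completes the definition without any new hepatocellular change, and the Protocol (5.1) itself describes bilirubin as a marker of progression risk in PBC.

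Long-term safety is the primary objective and there is one arm, so no control rate shows how many such flags the disease alone would produce.

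The other planned outputs do not separate these subjects. The shift tables use low, normal and high, so 1.1x ULN and 5x ULN are both high. The hepatic event of special interest (SAP 10.2.4) is defined by MedDRA query, not by laboratory values. SAP 10.8 plans no safety subgroups. The by-subject listings would let a reader trace a case, but would not change the tabulated number.

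**Working it through.** The plan states no expected number of Hy's law cases, so there is no figure to reproduce. The check applies the entry limits, the SAP rule and the Table 4 ALT/AST and bilirubin rows to example subjects. The INR, ALP and symptom rows were left out. One ULN per analyte, the SAP's, is used throughout.

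**Thresholds**
- Enzyme half of the rule: 3 × 45 = 135 U/L.
- Highest ALT admitted: 5 × 45 = 225 U/L.
- Bilirubin half: 2 × 12.3 = 24.6 µmol/L. The Protocol equates 3 mg/dL with 51.3 µmol/L, which is 17.1 per mg/dL, so this is 24.6 / 17.1 = 1.44 mg/dL.

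An eligible ALT of 135 to 225 U/L therefore meets the enzyme half at entry. For AST the range starts at 135 IU/L and has no listed upper limit.

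**Examples** (all within the ALT and bilirubin entry limits; the enzyme not shown is 40)

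| Enzyme, entry to later (U/L) | Bilirubin, entry to later (µmol/L) | SAP Hy's law | Table 4 combined row | Table 4 bilirubin row |
|---|---|---|---|---|
| ALT 180 to 180 | 10 to 25 | Yes | No (1.0x baseline) | Yes |
| AST 180 to 180 | 10 to 25 | Yes | No (1.0x baseline) | Yes |
| ALT 135 to 135 | 12.3 to 24.6 | Yes | No (1.0x baseline) | Yes |
| ALT 225 to 225 | 12.3 to 24.6 | Yes | No (1.0x baseline) | Yes |
| ALT 180 to 140 | 10 to 25 | Yes | No (0.78x baseline) | Yes |
| ALT 134 to 134 | 10 to 25 | No | No (1.0x baseline) | Yes |
| ALT 50 to 100 | 6.5 to 13.1 | No | Yes (2.0x and 2.02x baseline) | Yes |

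The fifth row is flagged although ALT improved. The last row is the converse: both values doubled, but ALT is only 100 / 45 = 2.2x ULN, so the SAP rule misses it.

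**Why the bilirubin row is always met.** If baseline bilirubin is at most 12.3, a later value of at least 24.6 is at least twice that baseline and above ULN. Any subject admitted under the bilirubin limit who meets the SAP rule therefore also meets Table 4's bilirubin row.

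**Size.** The documents do not give the share entering with ALT or AST at 3x ULN or more, or the share of those who later reach bilirubin of 2x ULN. Both are assumed here.
- 1% to 10% of 133 is 1.3 to 13.3 subjects. If 1% to 10% of these reach the bilirubin limit, that is 133 × 0.01 × 0.01 = 0.013 to 133 × 0.10 × 0.10 = 1.33 cases.
- 1% to 5% of 133 is 1.3 to 6.7 subjects. If 10% to 20% of these reach it, that is 133 × 0.01 × 0.10 = 0.13 to 133 × 0.05 × 0.20 = 1.33 cases.
- One case is 1 / 133 = 0.75%.

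**The case against.** The strongest reply is that a subject on the combination with an enzyme at 3x ULN or more, whose bilirubin has at least doubled to 2x ULN, belongs in a safety table whatever the cause. A laboratory table does not assign cause. Protocol 14.3 sends potential hepatic injury to independent adjudication, and the DMC sees the adjudicated results (15.9). This stands. It is the reason to keep the ULN-based count as the main one, and not to call these cases false.

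It also stands that few subjects may be affected. Subjects roll over while taking study drug. Exclusion 25, the Day 1 review and parent-study limits (not in these documents) may remove some with high AST or ALT.

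Three stronger readings may tempt a reader, and the documents do not support them:
- **That the rule counts cases before the first dose.** Its wording is not restricted to post-dose values, but entry excludes bilirubin above ULN. Only a case-by-case admission could produce a pre-dose case.
- **That the Protocol would ignore these subjects until ALT doubled.** That looks at one row of Table 4. The bilirubin row is met without any enzyme change.
- **That the SAP contradicts the Protocol.** Table 4 governs drug interruption and is not adopted as an analysis definition. Protocol 15.3 asks only that Hy's law be included in the laboratory summary, and the SAP does that.

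What the reply leaves untouched is that the planned table cannot distinguish a new joint rise from a bilirubin rise on stable enzymes, although the data to do so are already collected.

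**Conclusion.** The point holds as a weakness of tabulation. The SAP rule has no baseline term, entry allows ALT of 135 to 225 U/L and lists no AST limit, and a subject with unchanged or falling enzymes can therefore be counted once bilirubin reaches 24.6 µmol/L. It is not a gap in monitoring.

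The number affected is unknown and probably small: about 0 to 1 of 133 under the assumed rates, with most of the range below one subject. The thresholds and examples rest on the SAP's ULNs also being those applied at entry. It would go too far to say that one such case would decide the hepatic safety conclusion, given adjudication, the listings and DMC review. Even so, a single Hy's law case draws attention in a single-arm safety study. It is better to fix how such cases are shown before the data are seen than to explain them afterwards. This is a cheap improvement, not a condition for the study's validity.

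**What to change.** In SAP 10.3:

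1. Keep the ULN-based count as the main Hy's law result and state that it uses values after the first dose in Study 977-311.
2. Show that count separately, with denominators, for subjects whose baseline ALT and AST are both below 3x ULN and for those with either at or above 3x ULN.
3. For subjects with ALT or AST elevated at baseline, add a supplementary count using Table 4's combined row as written: ALT or AST at least 2x baseline with bilirubin at least 2x baseline. It should neither replace nor rename the main count. ALT going from 180 to 300 U/L is 6.7x ULN but only 1.67x baseline, so a rule that also demands a doubling would miss it even with high bilirubin. Conversely, the row has no ULN floor and will pick up subjects whom the main count does not.
4. State one baseline for the supplementary count: the last value before the first dose, as in SAP 5.1 and Protocol 15.3. The alternatives to rule out are the pre-dose mean in SAP 10.3 and the monitoring reset in Table 4 footnote b.

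The cost is a few lines of SAP text, one extra split of an existing table and one added count, with no new data. The downside is small cells.

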Blood samples for determining the plasma concentrations of OCA and BZF and their metabolites will be collected in this study.

Laboratory analyte results may be used to calculate various cardiovascular risk and fibrosis measurement scores.

The list of laboratory analytes to be tested is shown in Table 11.

Table 11: List of Laboratory Scores and Analytes

Laboratory Assessment	Scores and Analytes ^a
Serum chemistry	Albumin, ALP, BUN, creatinine, conjugated (direct) bilirubin, total bilirubin, AST (SGOT), ALT (SGPT), GGT, electrolytes [calcium, chloride, potassium, sodium], glucose, total protein, and blood lipids (total cholesterol, LDL, HDL and VLDL fractions and TG, magnesium, phosphorus, bicarbonate, unconjugated (indirect) bilirubin, free fatty acids, eGFR, CK, and CrCL
Hematology	Hemoglobin, hematocrit, white blood count with differential (neutrophils, lymphocytes, monocytes, eosinophils, basophils), platelets, and red blood cell count (including MCV, MCH, MCHC)
Urinalysis	pH, specific gravity, protein, glucose, ketones, bilirubin, blood, microscopic exam, creatinine, albumin, leukocytes, nitrates, and albumin/creatinine ratio (if positive)
Coagulation	PT, aPTT, INR
Noninvasive measurement of liver stiffness	ELF, and markers of [REDACTED] TE
Virology	HCV, HBsAg
Pregnancy test (female subjects of childbearing potential) ^b	β -hCG
Disease Severity Scores	MELD, CP, GLOBE and UK-PBC scores
PD assessment	[REDACTED]
PK assessment	BZF, OCA and their metabolites

[REDACTED]; aPTT=partial thromboplastin time; β -hCG=beta-human chorionic gonadotropin; BUN=blood urea nitrogen; BZF=bezafibrate; [REDACTED] CrCL=creatinine clearance; CK=creatinine kinase; CP=Child-Pugh score; eGFR=estimated glomerular filtration rate; ELF=enhanced liver fibrosis; HBsAg=hepatitis B surface antigen; HCV=hepatitis C virus; HDL=high-density lipoprotein; INR=international

normalized ratio; LDL=low-density lipoprotein; MCH=mean corpuscular hemoglobin; MCHC=mean corpuscular hemoglobin concentration; MCV=mean corpuscular volume; MELD=model of end-stage liver disease; OCA=obeticholic acid; PD=pharmacodynamic; PK=pharmacokinetic; [REDACTED] PT=prothrombin time; TE=transient elastography; TG=triglycerides; UK=United Kingdom; VLDL=very-low-density lipoprotein

^a Overlapping analytes will be analyzed only once.

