15.3.2. Clinical Laboratory Evaluations

Laboratory parameters and vital signs will be summarized using descriptive statistics at baseline (defined as the last assessment performed before the first dose of investigational product in Study 977-311) and at each scheduled postbaseline visit. The change from baseline will also be summarized. ECGs will be summarized using frequency at each visit. The shift from baseline will also be summarized. Baseline is defined as the mean of all available evaluations before treatment (except for lipoprotein assessments where Baseline will be Day 1).

In addition, shift tables from baseline based on normal ranges will be provided for hematology, coagulation, and serum chemistry to assess changes in laboratory values from baseline (Day 1) to each evaluation through Month 60 (EOS) or ET.

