10.2.4.3. Renal Impairment

Renal impairment is defined as events included in the following broad SMQs: acute renal failure, chronic kidney disease, proteinuria, renovascular disorders, or tubulointerstitial diseases.

Summaries will include a summary of the crude incidence of myalgia TEAEs and SAEs by system organ class and preferred terms.

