11. DEVIATIONS FROM PROTOCOL

There have been no deviations between the protocol-defined statistical analyses and those presented in this statistical analysis plan.

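### SAP 10.3 lists urine results without summarizing them, so sub-clinical change in urine protein or blood would appear in no table, and SAP 11 does not declare the departure from the protocol

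*SAP*

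**What the plan says.** Protocol 15.3.2 gives the general rule: "Laboratory parameters and vital signs will be summarized using descriptive statistics at baseline", and at each scheduled post-baseline visit. Section 15.3 says the same. Neither excludes urine and neither names it.

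Protocol 14.2.6, Table 11, lists urinalysis among the laboratory assessments, with these items: "pH, specific gravity, protein, glucose, ketones, bilirubin, blood, microscopic exam, creatinine, albumin, leukocytes, nitrates, and albumin/creatinine ratio (if positive". The last condition means that the albumin/creatinine ratio (ACR) is not measured in everyone. Table 3 marks urinalysis at every scheduled visit except Day 2.

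SAP 10.3 opens with the same general rule and later withdraws it for urine: "Urine chemistry and urinalysis results will not be summarized but will be provided in a data listing". It adds: "All clinical laboratory data (including central and local) will be presented in by-subject data listings". No reason is given for treating urine differently.

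SAP 10.2.4.3 defines the renal adverse event of special interest as "events included in the following broad SMQs: acute renal failure, chronic kidney disease, proteinuria", together with two further queries. SAP 11 states: "There have been no deviations between the protocol-defined statistical analyses and those presented in this statistical analysis plan".

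**The concern.** Two things look wrong.

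The first is an inconsistency. The protocol's rule covers laboratory parameters without exception, the SAP makes an exception for one panel, and the SAP then says that nothing differs.

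The second is what the exception removes. Long-term safety is the primary objective and follow-up runs to 60 months. The documents treat the kidney as worth watching: renal impairment is an event of special interest, potential renal injury is adjudicated (Protocol 14.3), and Protocol 5.4.2 says that about half of a bezafibrate dose leaves unchanged in the urine. But the event of special interest is built from coded adverse event terms. A urine result enters it only once someone has recorded an event. A modest drift in dipstick protein or blood across many subjects, none of them individually notable, would sit in a long listing where it is hard to see.

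**Working it through.** The plan states no figure on this point, so the check is a comparison of texts and a count of visits.

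**Which outputs would show a change in urine protein or blood?**

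| Output | Source | Shows urine protein or blood? |
|---|---|---|
| By-visit laboratory summaries | SAP 10.3 | No, urine is excluded |
| Laboratory shift tables | SAP 10.3 (hematology, serum chemistry) | No |
| Serum creatinine, eGFR, creatinine clearance | Table 11, under serum chemistry | No, these reflect filtration |
| Adverse event tables and the renal event of special interest | SAP 10.2.3, 10.2.4.3 | Only if recorded as an adverse event |
| Adjudicated renal events | Protocol 14.3 | Only for potential renal injury events |
| By-subject listing | SAP 10.3 | Yes, without aggregation |

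One class of finding has no aggregate output: urine change below the level at which it is recorded as an event.

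**How much data?** From Table 3:

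- Scheduled visits: Day 1, Day 2, M1, M3, M6, M12 (6), then M18, M24, M30, M36, M42, M48, M54, M60 (8). Total 6 + 8 = 14.
- Visits with urinalysis: 14 − 1 (Day 2) = 13, of which 12 are post-baseline.
- With all of the approximately 133 planned subjects completing: 133 × 13 = 1,729 samples, of which 133 × 12 = 1,596 are post-baseline.

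These are ceilings. A subject who withdraws has an early termination urinalysis but misses at least M60, so the total for that subject cannot exceed 13 either. Unscheduled tests would be extra.

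**Does the protocol promise each part of the remedy?** The by-visit summary follows from the general rule in 15.3 and 15.3.2. A urine shift table does not: 15.3.2 says "shift tables from baseline based on normal ranges will be provided for hematology, coagulation, and serum chemistry", and urine is not among them.

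**Two neighbouring slips found in the same check.** SAP 10.2.4.3, under Renal Impairment, specifies a summary of *myalgia* events, so the section sets out no summary of renal events. SAP 10.3 also leaves coagulation out of its shift tables, although the protocol names it. The second is a further undeclared difference bearing on SAP 11.

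**The case against.** The case for leaving the SAP alone is substantial.

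- The protocol's sentence is generic and no analysis section names urinalysis. Protocol 15 leaves the details to the SAP, so narrowing the rule there can be read as specification.
- Urine findings have a route into tables. Protocol 14.2.6 sets criteria for clinical significance, namely suspected new or worsened disease or organ toxicity, or a need for active management. Significant changes not already tied to an adverse event are to be recorded as one.
- Filtration markers are summarized, renal injury is adjudicated, and the monitoring committee reviews laboratory results roughly quarterly and at least every 6 months (Protocol 15.9).
- The risk tables in Protocol 5.6.2 list neither proteinuria nor haematuria as a known risk, and the nephrotic syndrome exclusion is an entry criterion. It is not evidence of an expected on-treatment signal.
- An ACR measured only when positive gives a selected, changing denominator.

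Most of this stands, and it rules out a stronger reading. A reader might infer that urine data are never analysed, or that progressive renal decline over 5 years would go unreported. The documents do not support either: results are listed, recognised events are tabulated, and falling filtration would show in the summarized serum measures.

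What the objection does not reach is change that is real in aggregate but minor in each subject. The serum measures do not capture urine protein or blood, and both adverse event recording and adjudication start from a recognised event. Nor does it explain why SAP 11 is silent.

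**Conclusion.** The point holds in a limited form. SAP 10.3 departs from the protocol's unqualified rule on laboratory summaries and SAP 11 does not say so. The practical loss is confined to sub-clinical change in urine protein and blood, collected at up to 13 scheduled visits per subject, 12 of them post-baseline.

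The figure of 1,729 samples assumes 133 subjects who all complete 60 months with no missed visits. It measures data without a planned summary. It is not a count of missed signals, and the documents give no basis for estimating one. No estimate is biased and no design feature is affected. The change is worth making because long-term safety is the primary objective, proteinuria falls within an event of special interest, and the data are already being collected.

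**What to change.** In SAP 10.3, replace the urine sentence with the following provisions.

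- **Urine protein and blood:** summarize at baseline and each scheduled visit, as counts and percentages by reported category, or with descriptive statistics if the laboratory reports quantities. The documents do not say which applies.
- **Shift:** add a categorical shift from baseline to worst post-baseline value for these two items. State whether unscheduled results count towards the worst value, since SAP 5.5 restricts analyses to scheduled visits. This table is an addition that the protocol does not promise.
- **ACR:** report only the number tested and the number abnormal at each visit, with the denominator shown. By-visit means would describe a selected group.
- **Other urine items:** keep in listings.

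In SAP 11, declare whatever remains listing-only and give the reason. At the same time, correct the reference to myalgia in SAP 10.2.4.3 to renal impairment, and either restore coagulation to the shift tables or declare its omission.

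If the sponsor prefers to list all urine results, declaring that in SAP 11 with a reason would cure the inconsistency but leave the reporting gap.

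The cost is SAP wording and one or two extra tables, with no new data collection and no change to study conduct.
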